6.7.2.2. Dose Modifications

Dose modification of azacitidine may not occur for participants in the initial 28-day period (Cycle 1).

Dose modifications described below are in accordance with the azacitidine prescribing information references, with 1 notable exception: while the US prescribing information allows for dose escalation to 100 mg/m² after the first 2 cycles, an azacitidine dose of 75 mg/m² is planned throughout this study for both treatment arms. Azacitidine dose increases above 75 mg/m² are not allowed. Dose modification guidance for azacitidine should be followed identically for both the experimental and control arms.

6.7.2.2.1. Dose Modification due to Hematologic Toxicity

6.7.2.2.1.1. Dose Modification in the Presence of MDS Disease

Treatment with azacitidine is associated with anemia, neutropenia, and thrombocytopenia. Thus, CBCs will be performed as described in the schedules of assessments and as needed to monitor toxicity. Importantly, these cytopenias are often a result of underlying hematological disease. It is thus critical to distinguish between cytopenias due to azacitidine compared to underlying disease, so as to not limit potential treatment benefit. Hematologic cytopenias in the presence of MDS disease are not defined as hematologic toxicities.

In accordance with this distinction, the dose of azacitidine will not be reduced if hematologic cytopenias are observed in the presence of MDS disease, defined by any of the criteria below:

- > 5% blasts in the bone marrow
- circulating blasts

Nonhematologic toxicities may require dose modifications independent of the presence of MDS disease, given the clearer distinction of these toxicities relating to azacitidine as opposed to effects of MDS. Dose modifications for hematologic toxicity, decreased bone marrow cellularity, and nonhematologic toxicities are described in the sections below.

6.7.2.2.1.2. Dose Modifications Due to Hematologic Toxicity in the Absence of MDS Disease

Azacitidine should be dose modified or delayed for hematologic toxicities without evidence of MDS disease (defined in Section 6.7.2.2.1).

If hematologic toxicity is observed following azacitidine treatment, the next cycle of therapy should be delayed for up to 14 days until the platelet count and the ANC have improved. If recovery is achieved within 14 days, no dose adjustment is necessary. However, if recovery is not achieved within 14 days (Day 42 of the cycle), the dose should be reduced according to [Table 11](#) and [Table 12](#). Following dose modifications, the cycle duration should return to 28 days. Participants with a dose reduction will be reassessed after 2 additional cycles per protocol. For participants with persistent cytopenia (as defined in [Table 11](#) and [Table 12](#)), treatment should be delayed for up to 14 days (Day 42 of the cycle); if counts have recovered, no further dose modification is needed. If counts have not recovered, then a further dose reduction is recommended, in accordance with [Table 11](#). The reduced dose should be maintained during subsequent cycles unless further toxicity develops (defined in [Table 11](#) as further occurrences). Azacitidine may be re-escalated back to a higher dose if toxicities have improved.

Separate dose modifications for hematologic toxicity are provided in [Table 11](#) for participants who do not have reduced blood counts at baseline ($ANC \geq 1.5 \times 10^9/L$ and platelets $\geq 75 \times 10^9/L$) and who have reduced baseline blood counts ($ANC < 1.5 \times 10^9/L$ or platelets $< 75 \times 10^9/L$).

Table 11. Azacitidine Dose Modification for Participants With and Without Cytopenia in the Absence of MDS

Nadir Counts		% Dose in the Next Cycle if Recovery ^a Is Not Achieved Within 14 Days
ANC ($\times 10^9/L$)	Platelets ($\times 10^9/L$)	
Dose Modification for Participants Without Reduced Blood Counts (ANC $\geq 1.5 \times 10^9/L$ and Platelets $\geq 75 \times 10^9/L$)		
First occurrence		
≤ 1.0	or ≤ 50.0	67% (50 mg/m ²)
Second occurrence^b		
≤ 1.0	or ≤ 50.0	50% (37.5 mg/m ²)
Third occurrence^b		
≤ 1.0	or ≤ 50.0	33% (25 mg/m ²)
Dose Modification for Participants with Reduced Blood Counts (ANC $< 1.5 \times 10^9/L$ or Platelets $< 75 \times 10^9/L$)		
First occurrence		
$< 0.5^c$	or $< 25^c$	67% (50 mg/m ²)
Second occurrence^b		
$< 0.5^c$	or $< 25^c$	50% (37.5 mg/m ²)
Third occurrence^b		
$< 0.5^c$	or $< 25^c$	33% (25 mg/m ²)

Abbreviation: ANC = absolute neutrophil count; MDS = myelodysplastic syndrome.

- a Recovery is defined as a $\geq 25\%$ recovery in the nadir count.
- b After initial dose reduction, participants will be reassessed after 2 additional cycles per protocol, and if persistent cytopenias are observed, a further dose reduction of azacitidine should be considered as outlined.
- c No dose adjustment is needed if the baseline blood counts are below an ANC $< 0.5 \times 10^9/L$ and/or platelets $< 25 \times 10^9/L$.

Following dose modifications, the cycle duration should return to 28 days.

6.7.2.2.2. Dose Modifications Due to Decreased Bone Marrow Cellularity in the Absence of MDS Disease

Azacitidine alone or in combination with magrolimab may result in a decrease in bone marrow cellularity. No dose modification is required if a decrease in bone marrow cellularity is observed without reduced peripheral blood counts or if MDS disease is still observed (as defined in Section 6.7.2.2.1). If hypocellularity AND reduced peripheral blood counts are observed, then the azacitidine dose should be modified in accordance with the instructions in Table 12.

Table 12. Azacitidine Dose Modification: Participants with Reduced Bone Marrow Cellularity and Reduced Peripheral Blood Counts in the Absence of MDS

Bone Marrow Cellularity	Azacitidine Dose Instruction if Recovery ^b Is Not Achieved Within 14 Days			
	First Occurrence	Second Occurrence	Third Occurrence	Recovery ^b

≥ 50% decrease from baseline with a cellularity < 30% in the presence of reduced peripheral blood counts^a
 
OR
 
Decrease to < 15% cellularity with a baseline cellularity > 20% in the presence of reduced peripheral blood counts^a
	
Dose reduce azacitidine to 50 mg/m² administered Days 1–7 per cycle
 
AND
 
Repeat bone marrow biopsy to assess bone marrow cellularity after 2 cycles.
	
Dose reduce azacitidine to 37.5 mg/m² administered Days 1–7 per cycle
 
AND
 
Repeat bone marrow biopsy to assess bone marrow cellularity after 2 cycles.
	
Dose reduce azacitidine to 25 mg/m² administered Days 1–7 per cycle
 
AND
 
Repeat bone marrow biopsy to assess bone marrow cellularity within 2 cycles.
 
Upon reassessment after 2 cycles, if reduced cellularity persists, then decrease azacitidine dose to 25 mg/m² on Days 1–5 per cycle and reassess bone marrow cellularity after 2 cycles.
	
Continue at current azacitidine dose. For subsequent cycles, the azacitidine dose can be escalated up to the next highest dose (i.e., escalate to 75 mg/m² if initially dose reduced to 50 mg/m²; escalate to 50 mg/m² if previously dose reduced to 37.5 mg/m²; or escalate to 37.5 mg/m² if previously dose reduced to 25 mg/m²).
 
AND
 
Repeat bone marrow biopsy to assess bone marrow cellularity at the next protocol-defined bone marrow assessment.

Abbreviation: ANC = absolute neutrophil count; MDS = myelodysplastic syndrome

a Reduced peripheral blood counts are defined as ANC < 0.5 × 10⁹/L and platelets < 25 × 10⁹/L in the absence of MDS disease (i.e., < 5% bone marrow blasts).

b Recovery in bone marrow cellularity is defined as an increase in bone marrow cellularity ≥ 25% from the nadir, increase in bone marrow cellularity to ≥ 15%, or improvement of peripheral blood counts to ANC > 0.5 × 10⁹/L and platelets > 25 × 10⁹/L.

Following dose modifications, the cycle duration should return to 28 days.

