6.7.2.1. Treatment Delays

After the initial 28-day period, in the absence of MDS disease (as defined in Section 6.7.2.2.1), if hematologic toxicity is observed following azacitidine treatment, the next cycle of treatment should be delayed until platelets are $\geq 50 \times 10^9/L$ and neutrophils are $\geq 1.0 \times 10^9/L$ or if blood counts are improving from nadir or baseline. If recovery is achieved within 14 days, no dose adjustment is needed. However, if recovery is not achieved within 14 days, the dose should be reduced according to the azacitidine dose modification guidelines in Section 6.7.2.2.1.2. For nonhematologic AEs \geq Grade 3 that do not resolve to \leq Grade 2 or baseline value, dosing will be delayed up to 14 days from onset. If recovery is achieved within 14 days, no dose adjustment is needed. However, if recovery is not achieved within 14 days, the dose should be reduced according to the azacitidine dose modification guidelines in Section 6.7.2.2.3. Following dose modifications, the cycle duration should return to 28 days. Azacitidine dosing may also be delayed for participants who experience hospitalization due to an AE that may preclude safe administration of azacitidine (e.g., intensive care unit admissions, significant bleeding events, severe infections, or other such events).

If ≤ 2 doses of azacitidine are missed during the 7-day dosing period, dosing should continue so that the participant receives the full 7 days of treatment, as long as these additional doses are given within 1 week of the previous dose. If ≥ 3 doses of azacitidine are missed during the 7-day dosing period, the Investigator should contact the Sponsor, and a dosing decision should be made on an individual case basis.

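### Table 12 footnote a defines absence of MDS disease by marrow blasts alone, contradicting the two-part definition that Section 6.7.2.2.2 adopts for that table

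*Protocol*

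**What the plan says.** Protocol Section 6.7.2.2.1.1 sets the governing rule: "the dose of azacitidine will not be reduced if hematologic cytopenias are observed in the presence of MDS disease, defined by any of the criteria" that follow. Two criteria are listed, marrow blasts above 5% and circulating blasts, and either is enough. The same section adds: "Hematologic cytopenias in the presence of MDS disease are not defined as hematologic toxicities".

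Other rules in Section 6.7.2 point back to this definition. The delay rule in Section 6.7.2.1 applies "in the absence of MDS disease (as defined in Section 6.7.2.2.1"). The hematologic-toxicity rule in Section 6.7.2.2.1.2 applies "without evidence of MDS disease (defined in Section 6.7.2.2.1"). The text above Table 12, in Section 6.7.2.2.2, says that no dose modification is needed when cellularity falls without reduced peripheral counts, "or if MDS disease is still observed (as defined in Section 6.7.2.2.1"). Where hypocellularity and reduced peripheral counts occur together, it sends the site to Table 12.

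The table does not itself say what reduced peripheral counts are. Footnote a does: ANC below 0.5 × 10⁹/L and platelets below 25 × 10⁹/L, "in the absence of MDS disease (i.e., < 5% bone marrow blasts"). Circulating blasts appear neither in the footnote nor anywhere else in Table 12.

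**The concern.** The footnote's abbreviation for *that is* equates absence of MDS disease with a marrow count below 5%. It does not offer this as one example. Half of the governing definition is lost, in the one place where a term needed to apply the table is specified. Section 6.7.2.2.1.2 also treats Tables 11 and 12 as the source for what counts as persistent cytopenia, so a site has reason to read the footnote as a working threshold.

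What is at stake is one dosing decision: a reduction of azacitidine in a participant whose cytopenias the protocol attributes to disease. Section 6.7.2.2.1.1 explains that cytopenias caused by the drug must be told apart from those caused by disease so that potential benefit is not curtailed. The omitted criterion also matters elsewhere in the protocol: complete remission in Appendix B, Table 19 requires 0% peripheral blasts as well as marrow blasts of 5% or less.

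**Working it through.** The protocol gives no figure to reproduce, so the check compares two definitions.

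**Definitions**
- Section 6.7.2.2.1.1: disease present = (marrow blasts > 5%) OR (circulating blasts). Negating this, disease absent = (marrow blasts ≤ 5%) AND (no circulating blasts).
- Table 12 footnote a: disease absent = (marrow blasts < 5%).

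**Cases.** Every row assumes the Table 12 fall in cellularity, ANC below 0.5 and platelets below 25 × 10⁹/L, and no recovery within 14 days. The last condition is in the table's column header and applies to every step.

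| Marrow blasts | Circulating blasts | Sections 6.7.2.2.1.1 and 6.7.2.2.2 | Table 12 and footnote a read alone | Agree? |
|---|---|---|---|---|
| < 5% | No | Absent: reduce | Absent: reduce | Yes |
| < 5% | Yes | Present: do not reduce | Absent: reduce to 50 mg/m² | **No** |
| Exactly 5% | No | Absent: reduce | Not counted as absent: Table 12 not met | No (lesser) |
| Exactly 5% | Yes | Present: do not reduce | Not counted as absent: Table 12 not met | Yes |
| > 5% | Either | Present: do not reduce | Not counted as absent: Table 12 not met | Yes |

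The second row is the substantive conflict, with opposite instructions for the same participant.

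The third row matters less. A participant at exactly 5% without circulating blasts has no MDS disease under Section 6.7.2.2.1.1, so Table 11 still applies, and its first step is usually the same 50 mg/m². It would not be when baseline counts were already below Table 11's floor, because note c to that table then calls for no adjustment.

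**Size of a first-step reduction**
- Full dose: 75 mg/m² × 7 doses = 525 mg/m² per cycle. Both permitted schedules (Days 1–7, or Days 1–5 with Days 8 and 9) give 7 doses.
- First occurrence in Table 12: 50 mg/m² × 7 doses = 350 mg/m² per cycle.
- Difference: 525 − 350 = 175 mg/m², and 175 / 525 = 33%.

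Tables 11 and 13 also start at 50 mg/m², so 33% describes any first-step reduction. It says nothing about how often the footnote would cause one.

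**The case against.** The strongest reply is that the section text already settles the matter. The paragraph directly above Table 12 exempts anyone who still has MDS disease under the full definition, the table's title limits it to absence of MDS, and Section 6.7.2.2.1.1 is categorical that the dose is not reduced when circulating blasts are present. The footnote defines a different term, reduced counts, and read with that paragraph it does not bring the exempted participant back in. A wrong reduction would also need 14 days without recovery. Sites must notify the blinded Medical Monitor of planned dose delays, which is a point of contact even though it is not an approval step.

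All of that stands, and it limits the problem. It does not remove it. Section 6.7.2.2.2 sends participants to Table 12 on reduced peripheral counts, and only footnote a says what that means for this table. A footnote that a site must consult to apply the table should not contradict the section it implements, and nothing in the protocol or SAP gives a reason for a different rule here.

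A reader might infer that the protocol as a whole directs sites to under-dose participants with circulating blasts. It does not, because the section read in full says the opposite. A reader might also infer that a third of the azacitidine dose is lost because of the footnote. The documents do not support that either: the figure is the size of one step, and no frequency is given.

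**Conclusion.** The footnote is wrong as written. It is a minor internal inconsistency in a dosing rule. It gives the wrong instruction for one narrow group: marrow blasts under 5%, circulating blasts, the Table 12 fall in cellularity, both counts below the stated limits, and no recovery within 14 days. Even then a wrong reduction follows only if the site works from the table and footnote without the section text. That some sites may do so is an assumption; the documents do not say how sites use the table.

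Where it happened from full dose, the first step would be 350 instead of 525 mg/m² per cycle. It need not be permanent. On recovery, Table 12 provides: "For subsequent cycles, the azacitidine dose can be escalated up to the next highest dose". The number of participants affected cannot be derived from the documents and is probably small.

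A reader might extend the point to the efficacy comparison. The documents give no basis for that. Section 6.7.2.2 states: "Dose modification guidance for azacitidine should be followed identically for both the experimental and control arms". No sample size, event count or significance level depends on the footnote, and no effect on power, alpha or the comparison of arms is claimed.

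**What to change.** Reword Table 12 footnote a so that reduced peripheral blood counts keep the present ANC and platelet limits and apply in the absence of MDS disease as defined in Section 6.7.2.2.1 (i.e., ≤ 5% bone marrow blasts and no circulating blasts). This resolves both the circulating-blast conflict and the exactly-5% mismatch. No other text needs to change.

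The cost is one footnote, in the next amendment or a clarification letter to sites. No new data are needed: Table 4 note d already asks for peripheral blasts with the blood counts, and Table 8 lists them among the on-study analytes.

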6.7.2.2.3. Dose Modifications Due to Nonhematologic Toxicity Irrespective of Presence of MDS Disease

Renal abnormalities ranging from elevated serum creatinine to renal failure have been reported with rare frequency in participants treated with azacitidine. In addition, renal tubular acidosis, defined as a decrease in serum bicarbonate to < 20 mmol/L in association with an alkaline urine and hypokalemia (serum potassium < 3 mmol/L), has been rarely observed. If unexplained reductions in serum bicarbonate (< 20 mmol/L) occur, the azacitidine dose should be reduced by 50% on the next cycle. Similarly, if unexplained elevations in serum creatinine or blood urea nitrogen to ≥ 2-fold above baseline values and above the ULN occur, the next cycle should be delayed until values return to normal or baseline, and the azacitidine dose should be reduced by 50%. The reduced dose should be maintained during subsequent cycles unless toxicity develops.

For other azacitidine-related nonhematologic toxicities that are \geq Grade 3 that do not resolve to \leq Grade 2 or baseline levels, azacitidine dosing should be delayed up to 14 days until resolution to \leq Grade 2 or baseline levels. If \geq Grade 3 toxicities continue despite this dose delay, dose modification of azacitidine should be performed in accordance with [Table 13](#).

Table 13. Azacitidine Dose Modification: Nonhematologic Toxicities

Toxicity	Azacitidine Dose Instruction if Recovery ^a is Not Achieved within 14 Days		
	First Occurrence ^b	Second Occurrence ^b	Third Occurrence ^b
Grade 3 or higher nonhematologic adverse event	Dose reduce azacitidine to 50 mg/m ² administered Days 1–7 per cycle AND Reassess toxicity on subsequent cycle; if still persistent despite dose delay, proceed to second occurrence.	Dose reduce azacitidine to 37.5 mg/m ² administered Days 1–7 per cycle AND Reassess toxicity on subsequent cycle; if still persistent despite dose delay, proceed to third occurrence.	Dose reduce azacitidine to 25 mg/m ² administered Days 1–7 per cycle AND Reassess toxicity on subsequent cycle; if still persistent despite dose delay, then administer azacitidine at 25 mg/m ² on Days 1–5 per cycle. Reassess toxicity on subsequent cycle. Fourth occurrence and beyond: If toxicity still persists, then contact the Medical Monitor for azacitidine dosing instructions.

a Recovery is defined as improvement of nonhematologic toxicity to \leq Grade 2 or baseline value within 14 days of dose delay.

b Azacitidine may be dose-escalated back to the original dose or next higher dose level if there is resolution of the toxicity to \leq Grade 2 or back to baseline level.

Following dose modifications, the cycle duration should return to 28 days. Please notify the blinded Medical Monitor of any planned dose delays.

6.8. Treatment Assignment and Bias Minimization

This is a multicenter, randomized, double-blind study. Participants who successfully complete screening will be randomized and receive either magrolimab + azacitidine (experimental arm) or azacitidine + placebo (control arm).

6.8.1. Treatment Allocation

Treatment allocation/randomization will occur centrally using an IXRS. Participants will be assigned randomly in a 1:1 ratio to either the experimental arm or the control arm.

6.8.2. Randomization Strategy and Procedure

To achieve balance between treatment arms, randomization will be stratified according to the following factors:

Geographic region (US versus ex-US sites)

Baseline cytogenetic risk (very good/good/intermediate versus poor/very poor versus unknown) according to IPSS-R {[Greenberg 2012](#)}

Baseline bone marrow blast percentage ($\geq 10\%$ versus $< 10\%$)

6.8.3. Extent and Maintenance of Blinding

This is a double-blind study. Azacitidine will be administered in both treatment arms. Magrolimab and azacitidine will be administered in the experimental arm. For the control arm, azacitidine + placebo will be administered. During the study, the Investigators, treatment teams, the participants, study management team, and all personnel directly involved in the conduct of the study or data cleaning will remain blinded to treatment assignment unless the criteria for unblinding at the interim analyses are met (see Section [8.3.1](#) and Section [8.3.2](#)), with the exception of specified personnel who may be unblinded based on their study role as described below:

- The pharmacists at each site who prepare magrolimab or saline placebo will be unblinded to the treatment assignment and will keep this information confidential from the participants, Investigators, treatment teams, and the Sponsor's study team members or their designees (excluding the designated unblinded site monitors for investigational product accountability).
- An unblinded Medical Monitor is available to provide consultation on protocol deviations with respect to magrolimab dosing.
- Designated members of Gilead Clinical Operations who serve as liaison in communication between the Sponsor study team and the designated unblinded contract research organization (CRO) personnel (unblinded site monitors and unblinded trial managers) with respect to investigational drug management and Gilead oversight of CRO activities will be unblinded.
- The Pharmacokinetics File Administrator, or designee, in Bioanalytical Operations and/or Clinical Data Management who facilitates the data transfer of PK files between Gilead and vendors will remain unblinded. The personnel handling RO data will also be unblinded.
- Individuals in Pharmaceutical Development and Manufacturing who have an Unblinded Inventory Manager role in the IXRS for purposes of study drug inventory management will remain unblinded.

- Individuals in Global Patient Safety who are responsible for safety signal detection, investigational new drug safety reporting, and/or expedited reporting of suspected unexpected serious adverse reactions (SUSARs) may be unblinded to individual case data and/or group level summaries.
- The data monitoring committee (DMC) and the independent biostatistician and statistical programmers from an independent data coordinating center (IDCC) who are responsible for preparing interim tables, listings, and graphs for DMC review remain unblinded. Controlled access to the unblinded data are described in the DMC Charter.
- The laboratories that will store and/or analyze blood samples for conducting PK, ADA, and RO analysis will be unblinded.
- The external vendor who conducts the PK/ADA merge with clinical data will be unblinded. In addition, the vendor who performs the population PK and exposure response analysis may be unblinded, if needed.
- Regulatory Quality and Compliance personnel in Research and Development may also be unblinded for purposes of supporting quality assurance activities and/or regulatory agency inspections.

In the event of a medical emergency that requires breaking the blind to provide medical care to the participant, the Investigator may obtain treatment assignment directly from the IXRS for that participant. Gilead recommends, but does not require, that the Investigator contact the Gilead Medical Monitor before breaking the blind. Treatment assignment should remain blinded unless that knowledge is necessary to determine the participant's emergency medical care. The rationale for unblinding must be clearly explained in source documentation along with the date on which the treatment assignment was obtained. The Investigator is requested to contact the Gilead Medical Monitor promptly if any treatment unblinding occurs.

Data that may potentially unblind the treatment assignment (e.g., study drug plasma concentrations) will be handled with special care to ensure that integrity of the blind is maintained and the potential for bias is minimized. This may include making special provisions, such as segregating the data in question from view by the Investigators, study team, or their designees as appropriate until the study unblinding for the primary analysis.

